## 5. Inclusion/Exclusion Criteria

### *Inclusion Criteria*

- HIV infection: This study is examining linkage to HCV care and treatment, with a focus on ART modifications among people living with HIV; therefore, participants must have an HIV diagnosis. People with HIV have a different, accelerated HCV disease course than those with HCV only. People with HIV also have different levels of engagement in healthcare and resources to attend healthcare than the general population due to Ryan White policies. Finally, barriers to engaging in HCV care historically have been different among people with HIV due to particularly low efficacy of HCV treatment options.
- Chronic HCV infection: This study aims to improve linkage to HCV care and treatment in those who need it; therefore, all participants must be chronically infected with HCV. Acute HCV infection is not included in this study because its management and the treatment course are vastly different.
- Age 18+: Most HIV-positive patients at the Bartlett Specialty Practice are over the age of 25 years. Children under the age of 18 years will not be included because management of HCV is different in this population, who does not receive care at the historical Moore Clinic.
- Did not attend appointment with a viral hepatitis provider at Viral Hepatitis Clinic/Bartlett Specialty Practice in past year: The primary goal of this study is to improve linkage to HCV care among those who are not engaged in care; therefore, anyone who has not had a visit at the HCV clinic in the past 1 year will be considered not linked to care because they have not been assessed by an HCV-specific provider in the all-oral era of HCV treatment.
- Ability to speak English: The study team has limited resources to create study materials and provide the nurse case management intervention in multiple languages. The clinic population is primarily African American and Caucasian patients, with few patients speaking no English.
- At least one visit at the Moore HIV Clinic or Bartlett Specialty Practice in the past year: This study aims to test an intervention that can be used in an HIV primary care clinic setting. Participants will be recruited from their regularly scheduled HIV clinic appointments; therefore, those who have been to the clinic in the past year will be considered active clinic patients.

### *Exclusion Criteria*

- Pregnancy: Women who are pregnant will be excluded from this study because treatment of pregnant women with direct acting antivirals and/or ribavirin is not recommended.

Date: May 8, 2017

Principal Investigator: [name], MPH, NP

Application Number: IRB00081068

- Emergency medical care needed: If a potentially eligible patient requires emergency medical care at the time of the HIV clinic appointment, the study team will not enroll this patient in the study so that the patient can receive necessary care. The patient will be able to contact the study team at a later date if interested in the study.
- Unable to provide informed consent: Patients who are independently unable to provide informed consent will be excluded from this study to minimize the risk of coercion by the study team or other third parties.

## 6. Drugs/ Substances/ Devices

N/A

## 7. Study Statistics

### Analysis:

Data will be cleaned and efforts made to minimize the effects of missing data. All provider visits at Johns Hopkins are registered in the electronic medical record, so absence of a registered appointment during the study period will be considered non-attendance for the primary outcome variable. A computer-based data collection method will be used for data collection of independent variables in attempt to minimize missing data. Exploratory and descriptive analysis will be completed for all study variables. Variables will be tested for normality and examined with means and standard deviations or medians and interquartile ranges accordingly. Baseline characteristics comparing the two groups (usual care vs. intervention) will be assessed. Any differences between the groups will be adjusted for in further analysis. The significance level will be set at 0.05. All tests will be two-tailed and analyzed by intention-to-treat.

**Primary Outcome:** The primary outcome is linkage to care, measured by attendance at the Viral Hepatitis Center (either traditional care or an HCV-treating clinical trial) within 60 days of randomization (yes/no). This hypothesis will be tested using a two-sample z-test for the difference in independent proportions comparing the intervention to usual care groups.

**Secondary Outcome:** The secondary outcome is time to HCV treatment initiation, measured by the number of days from randomization to the date HCV treatment is initiated according to the medical record. Kaplan Meier estimates will be conducted to compare time to HCV treatment initiation between participants in the intervention group and the usual care group, and a log-rank test will be used to test the difference. Covariates (age, sex, race/ethnicity, HCV knowledge, substance use, fibrosis score, CD4+ T cell count, HIV viral load, care giving responsibilities, and participation in Cure Club) will be included in the Cox regression model. To account for a time to treatment initiation greater than the observed time period of 6 months, right censoring will be implemented for participants who have not initiated HCV treatment at the end of the 6-month period.

**Exploratory Analysis:** Binary logistic regression will be used to determine an effect on linkage to care controlling for differences in age, sex, race/ethnicity, HCV knowledge, substance use, fibrosis score, CD4+ T cell count, HIV viral load, care giving responsibilities, and participation in Cure Club. A correlation matrix will be used to assess multicollinearity of the independent variables, and those with a correlation of greater than 0.6 will be considered for removal from the model. The remaining covariates will be entered into the model first, followed by the independent variable of interest (intervention vs. usual care). To evaluate how much predictive

Date: May 8, 2017

Principal Investigator: [name], MPH, NP

Application Number: IRB00081068

power was added to the model by adding the variable(s) of interest, the change in likelihood ratio test will be evaluated.

**Exit Interview:** Descriptive statistics will be used to examine the overall satisfaction of participants in the study. One-way frequency analysis will describe the intervention group's perceptions of the intervention and the interventionist to inform future studies. Participant responses to the barriers to linking to HCV care and initiating therapy will be grouped into categories and compared between the intervention and control group using a categorical Chi-Square test to determine if there is any difference in quantity and category of barriers to accessing care.

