**Participant Consent:** Once the participant contacts the study team through a study flyer, letter, clinical trials database, or provider referral, the study will be explained with an emphasis on the use of random assignment to study groups. The consent process will be completed in a private area of the Bartlett Specialty Practice. To account for low levels of literacy, the study materials have been developed on a 5th grade reading level. Participants will also be given the option to have the consent form read aloud in its entirety. The consent form will be maintained in the study files and participants will be given the option of taking a copy of the signed consent form with them. They will be informed that retention of the form may lead to a breach of confidentiality if the information is shared with someone who does not already know their HIV and/or HCV status.

**Assessment of Protocol Comprehension Prior to Signing Consent:** After the consent form is read by the participant or aloud, the study team member will evaluate comprehension with three protocol-specific questions: 1) What are the problems we are trying to improve?; 2) How does this study plan to improve these problems?; 3) How will you be assigned to the different options in this study? We will deem the participant to have an acceptable level of comprehension based on his/her ability to answer those questions.

**Allocation:** This RCT will be conducted and reported following the CONSORT clinical trial guidelines. The study design is pictured in Figure 1. After recruitment and informed consent, patients will be randomized to the nurse case management intervention group or to the usual care group electronically. Participants will be randomized in a 1:1 fashion using REDCap, a secure online data collection program, to ensure balanced, random assignment to the intervention and usual care groups. REDCap employs a simple randomization technique. This strategy will ensure that the study team has no a priori knowledge of group assignment when enrolling and randomizing study participants.

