with scores of 20 or greater (severe) will be referred to their primary provider, or, if the primary provider is not available, the covering urgent provider of the day, for further evaluation before the study is continued.

All questions in the protocol will be asked in a private area and can be administered by a study team member in 30-45 minutes. In addition to the subject questionnaire, each instrument contains a section for the research team to interrogate the patient's medical record to verify specific pieces of the medical history. These variables of interest include:

- CD4+ T cell count
- HIV viral load
- Prescribed HIV treatment
- Year of HCV diagnosis
- HCV RNA
- Fibrosis score
- HCV genotype
- HCV referral history
- HCV appointment history
- HCV treatment initiation barriers
- Hopkins appointment no-show rate

In addition to baseline and outcome data collection, monthly activity logs will be collected for each study participant, independent of allocated study arm. The type, quantity, and content of all encounters with a study participant in the Johns Hopkins system will be recorded each month, including nurse visits. This will define usual care for Bartlett Specialty Practice patients. The type, quantity, and content of all Care2Cure study visits will also be recorded to define the dose of the intervention. Data will be collected from the study participant's Epic record and the interventionist's notes.

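### The rule to adjust for any baseline difference lets chance add covariates to the adjusted models, while two collected attendance-history variables are in neither covariate list

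*Combined protocol and SAP*

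**What the plan says.** Section 7 (Analysis) plans a comparison of baseline characteristics between the arms and then states: "Any differences between the groups will be adjusted for in further analysis". It gives no threshold for a difference, no set of candidate variables and no target model.

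The tests and models that follow are these:

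- Primary outcome, linkage within 60 days: "This hypothesis will be tested using a two-sample z-test for the difference in independent proportions". No covariates.
- Secondary outcome, time to HCV treatment: Kaplan-Meier estimates and a log-rank test, without covariates. A list of ten covariates "will be included in the Cox regression model".
- Exploratory analysis: a logistic model for linkage, "controlling for differences in age, sex, race/ethnicity, HCV knowledge, substance use, fibrosis score, CD4+ T cell count, HIV viral load, care giving responsibilities". Cure Club participation completes the list, so these are the same ten. A screening step follows: "those with a correlation of greater than 0.6 will be considered for removal from the model".

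Section 4 (Allocation) says: "REDCap employs a simple randomization technique". Section 4 (Data Collection Measures) lists variables to be taken from the medical record, among them "HCV appointment history" and "Hopkins appointment no-show rate". Neither is in either covariate list.

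**The concern.** Under simple randomisation, a baseline difference between the arms carries no information beyond chance. A rule that adjusts for whatever differs therefore selects variables by accident. A strong predictor that happens to be balanced is left out, and an irrelevant variable that happens to be imbalanced is put in. Because no threshold is stated, the decision that a variable differs would be made with the data in view.

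This matters most for variables that plausibly predict the outcome. The primary outcome is attendance at an appointment, and a patient's record of keeping appointments is an obvious candidate predictor. That record is collected, but under the written plan it would be used only if it fell out of balance. The odds ratio from a logistic model also depends on which covariates are in it, so chance would have some say in what the exploratory model estimates.

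**Working it through.** **1. The plan's own figure.** The inputs are 0.40 vs 0.60, two-sided alpha 0.05 and 80% power (section 7, Sample Size Justification).

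n = [1.960·√(2·0.5·0.5) + 0.842·√(0.24+0.24)]² / 0.20² = (1.386 + 0.583)² / 0.04 = 96.9, so 97 per group. The stated figure reproduces.

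Power at 100 per arm: Φ[(0.20·√100 − 1.386)/0.693] = Φ(0.886) = 81.2%. The primary test is adequately powered without covariates.

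**2. How often the rule would bite.** Eight of the listed record variables lie outside the ten: prescribed HIV treatment, year of HCV diagnosis, HCV RNA, genotype, referral history, appointment history, treatment initiation barriers and no-show rate. If a difference meant p below a cut-off and the variables were independent (neither is stated in the documents), the chance that at least one is flagged is:

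- p<0.05: 1 − 0.95⁸ = 34%
- p<0.10: 1 − 0.90⁸ = 57%

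If barriers are not a baseline variable, seven remain and the figures are 30% and 52%. The no-show rate alone would enter in 5%, 10% or 20% of trials at cut-offs of 0.05, 0.10 or 0.20, however strongly it predicts attendance.

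**3. Does appointment history vary among eligible patients?** Yes. Section 4 (Patient Population/Setting) counts 480 never-attenders: 390 never scheduled (81.3%) and 90 scheduled but never attended (18.8%). It also mentions patients with older visits, without a count. The inclusion criteria exclude only those seen in the past year.

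**4. What fixed adjustment would give.** This was simulated with 100 per arm, 40% vs 60%, and 40,000 trials per setting (Monte Carlo SE about 0.2 points). The estimate is a standardised risk difference from a logistic model with arm, no-show rate and three-level history. Assumptions: 20% attended more than 1 year ago and the rest split 390:90; no-show rate 0.5 SD higher in the scheduled-never-attended group; history odds ratios against never scheduled of 0.67 and 1.5 (with no-show odds ratio 1.5) or 0.5 and 2 (with 2.0 to 3.0).

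| No-show odds ratio per SD | z-test power, % | Adjusted power, % | Adjusted 95% CI half-width, points |
|---|---|---|---|
| neither variable predicts | 82.7 | 81.7 | 13.58 |
| 1.5 | 82.7 | 83.4 | 13.21 |
| 2.0 | 82.5 | 86.5 | 12.66 |
| 2.5 | 82.3 | 88.4 | 12.29 |
| 3.0 | 82.8 | 89.9 | 11.98 |

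The unadjusted half-width is 13.51 points. With the no-show rate as the only predictor, the gain is 0.0–0.2 points at odds ratio 1.5 and 2.6–2.8 at 2.0. With history alone it is 0.1–0.6 points.

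**5. The imbalance rule on the same two variables.** At odds ratio 2.0, its power is 83.1%, 83.4% and 84.0% at cut-offs of 0.05, 0.10 and 0.20, against 86.5% for fixed adjustment. Under the null it rejects in 4.1–5.2% of trials; the z-test and the fixed adjustment reject in 4.9–5.4%.

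**6. Inside the planned logistic model.** With ten covariates already present, assumed non-prognostic, adding the two variables raises power from about 80% to 82%, 85% and 89% at no-show odds ratios of 1.5, 2.0 and 3.0. The imbalance rule stays at 79–82%.

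**7. Effect on the odds ratio.** Unadjusted, 0.40 vs 0.60 gives (0.6/0.4)/(0.4/0.6) = 2.25. Hold those rates fixed, add one normal covariate with odds ratio 1.5, 2.0, 2.5 or 3.0 per SD, and solve for the two arm intercepts by numerical integration. The conditional odds ratio becomes 2.32, 2.46, 2.60 or 2.74.

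**The case against.** The strongest reply is that nothing the trial tests is touched. Both the z-test and the log-rank test are unadjusted, so only the Cox model and a model labelled exploratory remain. That stands. A reader might infer from the rule that the primary result is open to manipulation or that false-positive risk rises. The documents do not support this: the primary test is named and takes no covariates, and the rule applied mechanically does not raise the rejection rate under the null. A reader might also infer that the adjusted models are wholly unspecified. They are not: ten covariates are named, and the literal rule can only add to them.

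Second, the exploratory paragraph speaks of "controlling for differences in age, sex, race/ethnicity, HCV knowledge, substance use, fibrosis score, CD4+ T cell count, HIV viral load, care giving responsibilities", which echoes the disputed sentence and suggests that it may mean no more than the listed ten. That reading is fair, but the sentence then does no work and can still go.

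Third, the gains are measured against a z-test that stays primary, and they rest on assumed predictor strengths, with no-show and history effects strengthened together. The 390:90 split describes clinic patients in May 2015, not enrolled participants. All of this stands and limits the claim. The ten-covariate check in step 6 answers part of it. The odds-ratio shift in step 7 starts from a model with no covariates, so it illustrates the mechanism and does not give its size in the planned model.

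Fourth, the 34% and 57% depend on a threshold and an independence that the documents do not give, and the count of eight is debatable. They are illustrations only.

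**Conclusion.** The point holds for the adjusted models only. Read literally, the sentence lets chance imbalance extend a covariate list that is otherwise fixed; read mildly, it is redundant. The two collected variables most plausibly related to an attendance outcome are left out of both lists, so the no-show rate would be used in about 5% of trials if p<0.05 were the cut-off.

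The benefit of fixing this is precision in a supportive estimate: about 1 point of power lost if neither variable predicts, and about 1, 4 and 7 points gained at no-show odds ratios of 1.5, 2.0 and 3.0 per SD combined with the assumed history effects. The documents give no predictor strengths, so where the trial would fall in that range is unknown. The sample size and both planned hypothesis tests stand as written.

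**What to change.** - Delete the imbalance sentence and report baseline comparisons descriptively.
- Keep the z-test as the primary analysis.
- Prespecify one supportive risk difference for 60-day linkage with its 95% CI, by standardisation from a logistic model with arm, Hopkins no-show rate and HCV appointment history.
- Take both covariates as they stood before randomisation. State the look-back window for the no-show rate. Code history as never scheduled, scheduled but never attended, and attended more than 1 year ago.
- Add both variables to the exploratory logistic list, and state that they are fixed and exempt from the removal step for correlations above 0.6.

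The cost is a few sentences and one more linkage analysis to report. No new data are needed beyond fixing the abstraction date, the look-back window and the coding. Eligibility requires a clinic visit in the past year, so a look-back of at least 12 months should leave few missing no-show rates, although some will rest on few appointments. The downside is reliance on a simple working model and about 1 point of power lost in the supportive analysis if neither variable predicts attendance.

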### **Sample Size Justification:**

Currently, 40% of new Viral Hepatitis Clinic appointments are attended by patients. Based on prior studies testing the intervention components in similar populations, including persons living with HIV and/or substance use disorders, it is expected that the intervention will improve the primary outcome of linkage to care by 18-30%. Although the effect size is not known in the context of HCV, we estimate an improvement in linkage of 20% (i.e., 60% attendance [0.60] in the NCM group compared to 40% attendance [0.40] in the usual care group) based on these prior studies. Using these figures and a two-tailed test with an alpha of 0.05, a conservative estimate of the total sample size required to achieve 80% power is 97 per group, or a total of 194 participants (G\*Power 3.1.9.2). With a sample size of 100 participants in each group, there should be an adequate number of participants to detect a difference in proportion of linkage to care for the primary aim.

For Phase 2, participants with successful linkage to clinical care from Phase 1 (those who attend  $\geq 1$  appointment at the Viral Hepatitis Clinic within 60 days) will be included. Therefore, the eligible sample size will be less than 40-60% of the original sample size because a linkage to care proportion of 0.40-0.60 is expected, and some participants will link to a clinical trial and not be included in this outcome. This is a secondary outcome and estimated effect size is unknown. However, with 100 participants in this group (half of the total sample size), we will have 90% power to detect a hazard ratio of 2.

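### The primary linkage test is valid but unadjusted; a pre-specified, covariate-standardised risk difference would put baseline data the trial already collects to use

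*Combined protocol and SAP*

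**What the plan says.** The primary outcome in section 7 is attendance within 60 days of randomisation, yes or no. The only primary test named is unadjusted: "This hypothesis will be tested using a two-sample z-test for the difference in independent proportions comparing the intervention to usual care groups". Two general rules apply: "The significance level will be set at 0.05" and "All tests will be two-tailed and analyzed by intention-to-treat". The Sample Size Justification assumes "60% attendance [0.60] in the NCM group compared to 40% attendance [0.40] in the usual care group" and arrives at "a conservative estimate of the total sample size required to achieve 80% power is 97 per group, or a total of 194 participants". Planned enrolment is 100 per group.

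Covariate adjustment appears in three other places in section 7:

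- **Exploratory Analysis:** "Binary logistic regression will be used to determine an effect on linkage to care controlling for differences in age, sex", followed by eight more covariates, ten in all, the last being participation in Cure Club. Covariates correlated above 0.6 are considered for removal, arm is entered last, and its contribution is judged by the change in the likelihood ratio test.
- **Opening paragraph of Analysis:** baseline differences found between the groups are to be adjusted for later. No analysis, criterion or covariate is named.
- **Secondary Outcome:** the same ten covariates go into a Cox model for time to HCV treatment.

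The plan states no confidence interval for the difference in proportions, no adjusted risk difference, and no step that turns the logistic model into one.

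Section 4 describes the design and the data. "Participants will be randomized in a 1:1 fashion using REDCap", by simple randomisation with no stratification stated. Under Data Collection Measures, the trial records HCV knowledge by questionnaire. From the chart it takes HCV referral history, HCV appointment history and the appointment no-show rate. The no-show rate is not among the ten covariates in section 7.

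**The concern.** Two things are at stake.

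**Precision.** The outcome is attendance at an appointment, and the trial holds data that plausibly predict attendance, past no-show rate above all. Simple randomisation without stratification does nothing to limit chance imbalance in such factors, so only the analysis can deal with it. The power margin is thin, and the Sample Size Justification itself says the effect size is not known in the context of HCV.

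**Interpretation and pre-specification.** The trial will produce an unadjusted difference in proportions and a conditional logistic coefficient for the same outcome, with no stated link between them. A coefficient that moves away from the null after adjustment may be read as corrected confounding or a stronger effect, when it can be a property of the scale alone. Adjusting for observed differences, together with a correlation screen, also leaves the choice of covariates open until data are in hand.

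**Working it through.** **Inputs from the protocol (sections 4 and 7).** Linkage 0.40 and 0.60; two-sided alpha 0.05; 80% power; 1:1 allocation; 100 per arm planned. **Assumption not in the documents:** R2, the share of outcome variance explained by baseline covariates, taken over 0 to 0.20.

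**1. The plan's own sample size.** With pooled variance and no continuity correction,

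n per arm = [1.96 × √(2 × 0.5 × 0.5) + 0.8416 × √(0.24 + 0.24)]² / 0.20² = (1.3859 + 0.5831)² / 0.04 = 96.9, which rounds up to 97.

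This matches the plan exactly.

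**2. Power at 100 per arm, unadjusted.** SE under the null is √(0.50/100) = 0.0707. SE under the alternative is √(0.48/100) = 0.0693.

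Power = Φ[(0.20 − 1.96 × 0.0707) / 0.0693] = Φ(0.886) = 81.2%.

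Using the unpooled SE throughout gives Φ(0.20/0.0693 − 1.96) = 82.3%. The two bases differ by about one point and should not be mixed. The figures below are pooled.

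**3. Power with adjustment.** Multiply both SEs by √(1 − R2). Equivalent unadjusted n per arm is 100/(1 − R2). The 95% CI half-width is 1.96 × 0.0693 × √(1 − R2).

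| R2 (assumed) | Power, 60% v 40% | Power, 58% v 40% | CI half-width | Equivalent n per arm |
|---|---|---|---|---|
| 0 | 81.2% | 72% | 0.136 | 100 |
| 0.05 | 83.2% | 75% | 0.132 | 105 |
| 0.10 | 85.1% | 77% | 0.129 | 111 |
| 0.20 | 89.0% | 82% | 0.122 | 125 |

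The 58% column takes the low end of the 18-30% improvement cited in the Sample Size Justification and reads it as percentage points, as that section does for its 20%.

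**4. Simulation check.** 200 participants, simple 1:1 randomisation, ten covariates, 4,000 runs per scenario. Power of the z-test against the standardised risk difference was:

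- 82.6% v 82.1% with non-prognostic covariates
- 81.8% v 83.0% at R2 about 0.05
- 81.2% v 87.5% at R2 about 0.17

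With no treatment effect, type I error was 5.7-6.6% for the standardised estimate and 4.9-5.8% for the z-test (Monte Carlo error about 0.7 points). Ten covariates is therefore somewhat long for 200 participants.

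**5. Scale.** The marginal odds ratio at the planning rates is (0.6/0.4)/(0.4/0.6) = 2.25. Holding the marginal rates at 0.40 and 0.60, with covariates perfectly balanced, the conditional odds ratio is 2.36, 2.49, 2.66 and 3.14 at R2 of about 0.05, 0.11, 0.17 and 0.29. Standardising the fitted logistic model gave mean risk differences of 0.199 to 0.203 in the simulation, against a true 0.20. The same model can therefore report on the primary scale.

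**The case against.** The strongest reply is that nothing here is wrong. The z-test is valid under the stated randomisation, the sample size was built for it and reproduces, and planned enrolment meets the 80% target. All of that stands. A reader might infer that the primary test is faulty or the trial underpowered by its own criterion; the documents support neither.

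A reader might also infer that all adjustment has been pushed into an exploratory odds ratio. That goes too far. The secondary Cox model is adjusted, and section 7 promises adjustment for observed group differences. The exploratory paragraph names a likelihood-ratio test, not an odds ratio; the odds ratio is inferred from the choice of logistic regression. That promise of adjustment is no substitute for a plan, though, because it names no analysis and lets the data choose the covariates.

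Nor is it right that the two linkage results can never be compared. Standardisation puts them on one scale; they are only not directly comparable as planned. The logistic model also serves Aim 3, on characteristics associated with uptake of care, at least in part, and the plan never offers it as a check on the primary difference.

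Finally, the gain depends on an R2 that the documents do not give, and with non-prognostic covariates simulated power fell by half a point. Adjustment also needs a rule for missing covariates, which the present primary analysis does not, because an unregistered visit counts as non-attendance. Both points are fair. They argue for a short list and a stated rule, not against adjustment.

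**Conclusion.** The point holds as a recommended improvement in efficiency and pre-specification. The planned test is sound and has 81.2% power at 100 per arm, but it leaves unused baseline values that may be prognostic, and the plan fixes no adjusted analysis on the primary scale.

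At the planning rates the possible gain is about 2 points of power at R2 = 0.05, 4 at 0.10 and 8 at 0.20, with essentially none at 0. It would matter most if the true effect lies near 18 points, where unadjusted power is about 72%. The documents do not allow anyone to say how much precision is actually forgone, so a flat statement that the trial throws precision away is not supported. The scale point does not depend on imbalance: it applies whenever the covariates are prognostic.

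**What to change.** Make the primary analysis the covariate-standardised difference in linkage proportions:

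- Fit a logistic model with arm and a short, fixed list of baseline covariates, for example age, sex, HCV knowledge, substance use and prior no-show rate, each recorded before allocation.
- Average the predicted risks over all randomised participants under each arm. Report the difference with a robust or delta-method SE, a 95% CI and a two-sided test at 0.05.
- Fix the list before outcome data are seen. Do not choose covariates by observed imbalance or by the 0.6 correlation screen, and remove or tie down the open promise to adjust for group differences.
- Leave out Cure Club participation. Section 4 (Phase 1) names the group as a possible referral within the intervention, so it can follow randomisation, and conditioning on it could bias the effect.
- State a simple rule for missing baseline values, applied without regard to arm, so that all 200 participants stay in the analysis.
- Report the unadjusted risk difference with its CI, and the z-test, as the sensitivity analysis. The exploratory logistic model can remain for Aim 3.

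The cost is SAP wording and slightly more programming, with no extra participants or data collection. The downside is a negligible loss of power if the covariates are not prognostic, and slight type I inflation if the list is long, which is the reason to keep it short.
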